8.6 Trial outcome measures

8.6.1 Primary outcome measure

Clinically relevant VTE within 30 days from randomisation, including any confirmed diagnosis of symptomatic DVT, pulmonary embolism, or death related to VTE.

The definition of ***clinically relevant*** VTE is as follows:

- Any ***symptomatic*** DVT or PE event where the treating team has made a working diagnosis for a DVT or PE based on symptoms and or clinical signs and subsequently investigations requested to verify the diagnosis (e.g., ultrasound / CT pulmonary angiogram (CTPA)).

DVT or PE occurrence

Symptomatic DVT or PE will be investigated as per standard clinical practice either by compression Doppler ultrasound of the femoral and popliteal veins or CTPA, as appropriate.

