8.6.2 Secondary outcome measures

- Proximal DVT at asymptomatic screening ultrasound (*only relevant for sites where they undertake screening ultrasound as part of routine clinical practice*)
- Progression of intracranial haemorrhage within 14 days after randomisation requiring neurosurgical intervention
- Progression of intracranial haemorrhage on routinely performed imaging
- Adverse events, of special interest (AESI) including major and clinically relevant bleeding events (bleeding events are assessed and reported in accordance with criteria published by the International Society of Thrombosis and Haemostasis) (see Appendix 1)
- VTE at 90 days
- 7-day, 30-day, and 12-month mortality
- Glasgow Outcome Scale-Extended (GOS-E) at 6 and 12 months

- Quality of life (EQ5D-5L) at Day 30 or discharge, 6 and 12 months
- Length of stay of index admission
- Economic analysis (see section 16.5)

Given patients with TBI are prone to VTE events, some hospital practices undertake a screening ultrasound to investigate for asymptomatic DVTs. Sites will be allowed to perform screening ultrasound at their discretion; however, this trial will only include **asymptomatic proximal DVT** diagnosed by ultrasound. A proximal DVT is defined as a DVT that is in the popliteal, femoral or iliac veins. A DVT that is located below the knee and is confined to the calf veins (peroneal, posterior, anterior tibial, and muscular veins) without a proximal component will not be recorded. This is because up to 25% of patients admitted to an intensive care environment can have asymptomatic distal DVTs that are of no clinical relevance.

The trial will allow any **asymptomatic proximal DVT** as part of asymptomatic screening ultrasound diagnosed from the day of randomisation up until day 29 post randomisation. This will be recorded as a secondary outcome.

9. Selection and withdrawal of participants

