9.3 Treatment assignment

Patients who fulfil the eligibility criteria will be randomly assigned to the early pharmacological thromboprophylaxis (PTP) administration arm (<72 hours) or the late PTP administration arm (prescription of PTP deferred by a minimum of 120 hours or PTP not prescribed if deemed unnecessary by the clinical team).

Masking

It will not be possible to mask the intervention as we consider it unsafe, impractical, and costly. For example, if there is progression of an intracranial haemorrhage it is important for the clinical team managing the patient to understand the timing and number of doses administered of PTP for patient safety and to guide decision making on use of reversal agents. Our design includes blinded assessment of several secondary outcomes (e.g. GOS-E) to minimise bias from knowledge of treatment assignment.

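### Screening ultrasound is left to site discretion in an open trial, and its findings are kept out of the primary outcome; no rule makes scanning independent of allocation or has scans counted by arm

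*Protocol*

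**What the plan says.** Section 8.6.1 defines the primary outcome as "Clinically relevant VTE within 30 days from randomisation, including any confirmed diagnosis of symptomatic DVT, pulmonary embolism, or death related to VTE". A DVT or PE qualifies as an "event where the treating team has made a working diagnosis for a DVT or PE based on symptoms and or clinical signs", with imaging then requested to verify it.

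Section 8.6.2 lists proximal DVT on asymptomatic screening as a secondary outcome, "only relevant for sites where they undertake screening ultrasound as part of routine clinical practice". The text below the list adds: "Sites will be allowed to perform screening ultrasound at their discretion". An asymptomatic proximal DVT counts if "diagnosed from the day of randomisation up until day 29 post randomisation", which is nearly the whole primary window, and "This will be recorded as a secondary outcome".

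On masking, Section 9.3 states: "It will not be possible to mask the intervention as we consider it unsafe, impractical, and costly". It continues: "Our design includes blinded assessment of several secondary outcomes (e.g. GOS-E) to minimise bias from knowledge of treatment assignment". The primary outcome is not named there.

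Three other places bear on the point. Section 11.5.2 again links the screening assessment to sites that screen routinely. Section 9.3.3 says that prophylaxis initiation and timing are meant to be the sole planned difference between the arms. Section 9.3.4 stratifies by extracranial injury and by ward or critical care, not by site or screening practice. The schedule in Section 11.6 has no row for screening scans.

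**The concern.** Leaving asymptomatic DVT out of the primary outcome is defensible: counting it would let scanning intensity create events. The weakness is pairing that exclusion with scanning that takes place after randomisation, by teams who know the allocation, under no rule that it be the same in both arms.

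A proximal DVT that is found and managed before symptoms appear may never become a primary event, and that patient then enters the primary analysis as free of VTE. If scanning differs by arm, the primary estimate (the difference in absolute 30-day VTE rates, Section 15.1) partly reflects who was scanned. The secondary screening outcome is exposed too, because more scans in one arm find more DVT there. Without a record of scans by arm, neither effect could be recognised afterwards.

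**Working it through.** **Inputs from the protocol (Section 15.3).** Late 10%, early 5%, 5% level, 90% power, 1441 evaluable patients. I assume a two-sided test and 1:1 allocation, neither of which is stated.

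**The plan's own figures.** Per arm, n = [1.96·√(2p̄(1−p̄)) + 1.2816·√(p₁(1−p₁)+p₂(1−p₂))]² / (p₁−p₂)².
- 10% vs 5%: 581.1, so 582 per arm and 1164 in total, as stated.
- 12% vs 7%: 720.6, so 721 per arm and 1442 in total, against 1441 stated.

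The sample size reproduces; no stated figure is at issue.

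**Model for screening.** Let s be the share of an arm that is scanned and k the share of would-be primary events in scanned patients that the scan prevents. The protocol gives neither, so both are assumptions. With g = s·k, the observed risks are 0.10(1−g_L) and 0.05(1−g_E), and

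observed difference = 0.05 − 0.10·g_L + 0.05·g_E.

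Power = Φ[(d − 1.96·SE₀)/SE₁], with SE₀ = √(2p̄(1−p̄)/n), SE₁ = √((p_L(1−p_L)+p_E(1−p_E))/n) and n = 1441/2 = 720.5.

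Example, 30% scanned in each arm and k = 0.3: g = 0.09, so the risks are 9.10% and 4.55% and d = 0.0455. SE₀ = 0.01329 and SE₁ = 0.01323. Power = Φ[(0.0455 − 0.02604)/0.01323] = Φ(1.47) = 93%.

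| Scanned late / early | k | Late | Early | Difference (points) | Power |
|---|---|---|---|---|---|
| none | – | 10.0% | 5.0% | 5.0 | 95% |
| 30% / 30% | 0.3 | 9.10% | 4.55% | 4.55 | 93% |
| 40% / 20% | 0.3 | 8.80% | 4.70% | 4.1 | 87% |
| 20% / 40% | 0.3 | 9.40% | 4.40% | 5.0 | 96% |
| 50% / 20% | 0.5 | 7.50% | 4.50% | 3.0 | 67% |
| 20% / 50% | 0.5 | 9.00% | 3.75% | 5.25 | 98% |

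**Direction.** More scanning in the late arm lowers the difference. More in the early arm raises it relative to equal scanning (5.0 against 4.55 points in the 20%/40% row). Relative to no scanning at all, the difference rises only when g_E exceeds 2·g_L, because the late arm has twice the events to lose. Removing 20% of events from one arm only gives 3.0 points if late (8% vs 5%) and 6.0 points if early (10% vs 4%).

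**No true effect.** With 10% in both arms, removing 10%, 20% or 30% of events from one arm only raises the two-sided false-positive rate from 5% to about 10%, 26% or 53%.

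**The case against.** The best defence is that the protocol already leans towards equal care. The outcome lists and Section 11.5.2 tie the screening outcome to sites with routine screening, and Section 9.3.3 says all other care follows standard pathways. So it would be wrong to say that nothing links screening to site practice. A reader might also infer that Section 8.6.2 contains two contradictory rules. The text does not force that: the sentence about discretion follows one noting that some hospitals screen, and the two can be read as one rule under which such hospitals may carry on. What remains is narrower. The routine-practice wording limits where the secondary outcome applies, and the standard-care wording states an intention; neither says that scanning must ignore allocation.

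The mechanism is also an inference. Section 9.3.3 describes treatment only for symptomatic VTE, and Section 6.2 warns that therapeutic anticoagulation may complicate recovery after TBI, so k could be small. A patient with a screen-detected DVT who later develops symptoms can still meet the primary definition. Both points stand, and they limit the certainty of the effect.

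In a pragmatic trial, dilution under routine screening is arguably part of the effect being estimated, and the modest equal-scanning case keeps power above the planned 90%. That stands for equal scanning. It does not cover scanning prompted by the allocation.

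Finally, a supportive analysis may sit in a statistical analysis plan that is not shown, so its absence here is no fault. But an analysis plan cannot govern who is scanned or recover scans that were never recorded.

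**Conclusion.** The point holds as a gap in trial conduct that the protocol should close. Screening is discretionary, allocation is known, screen-detected proximal DVT lies outside the primary outcome, and no text makes scanning independent of allocation or has scans recorded by arm.

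A reader might infer that the trial is biased against early prophylaxis, on the reasoning that clinicians told to withhold it will scan more. The documents do not support a direction: nothing says which arm would be scanned more. Nor do they support any particular loss of power. The 67% figure needs 50% against 20% scanned and half of the events prevented, none of which the protocol states.

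The size is therefore unknown. Equal scanning dilutes the difference (5.0 to about 4.6 points in the modest case) and does little harm to planned power there. Unequal scanning is the real exposure, in either direction. All of this assumes that some screen-detected proximal DVTs are managed before they become symptomatic.

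**What to change.** 1. In Section 8.6.2, replace the discretion wording with a statement that each site declares its existing screening policy before opening (none, or a described routine) and applies that policy irrespective of allocation. State that no scans beyond that policy are required.
2. Record each screening scan and its indication in the eCRF, and report scans per patient by arm.
3. Leave the primary outcome unchanged. Add one supportive analysis counting symptomatic VTE, VTE-related death or screen-detected proximal DVT within the primary window, limited to or stratified by screening sites and read beside the scan rates by arm.

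The cost is amendment wording, a line in site set-up, an eCRF field and one analysis. Sites that now scan ad hoc would have to commit to a policy. The supportive analysis is itself sensitive to unequal scanning, so it cannot replace item 1 and should not be read without item 2.

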9.1 Inclusion criteria

- Adult patients (≥ 16 years of age)
- Acute TBI (defined as acute traumatic changes on the CT brain, either in isolation or in the context of polytrauma)
- Patients admitted to hospital within 72 hours of injury

9.2 Exclusion criteria

- Patients with recent VTE (within 3 months before TBI)
- Known hypersensitivity to any VTE prophylaxis agents used
- Patients are not expected to live beyond 72 hours
- The time interval from injury to randomisation exceeds 72 hours
- Participation in the same study within the last 12 months
- Current use of anticoagulation for an alternative indication, with a clinical decision to continue
- Active bleeding was deemed serious enough that the treating clinical team lacked equipoise for the study question
- Progression of early traumatic intracranial haemorrhage or unstable neurological condition, such that the treating clinical team lack equipoise for the study questions

Patients who fit the inclusion criteria and are on pre-existing anticoagulation (e.g. Warfarin for atrial fibrillation) should be managed as per standard hospital protocol. This would routinely involve stopping and reversing the agent. If there is a clinical indication to continue the anticoagulation for a reason other than for VTE prophylaxis, the patient will be excluded.

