Low molecular weight heparins (LMWH)	
• Drugs under this class include: dalteparin sodium, enoxaparin sodium and tinzaparin sodium• Preferred over heparin (unfractionated) in the prevention of VTE since they are as effective and have a lower risk of heparin induced thrombocytopenia• The prophylactic regime does not require anticoagulant monitoring• Duration of action is longer than heparin (unfractionated) thus once daily subcutaneous administration possible
Heparinoids	
• Drugs under this class include: danaparoid sodium• Used primarily for prophylaxis of DVT in patients undergoing general or orthopaedic surgery and patients who develop heparin induced thrombocytopenia
Fondaparinux sodium	
• Used for VTE prophylaxis in patients undergoing major orthopaedic surgery of the hip or leg or abdominal surgery or medical patients who are immobilised because of acute illness
Oral anticoagulants	
• Drugs under this class include: Apixaban, Rivaroxaban, Dabigatran, Edoxaban and Warfarin• Apixaban, Rivaroxaban, Dabigatran, Edoxaban are licenced for the prevention of recurrent DVT and PE in adults• Warfarin is licenced for prophylaxis for DVT and PE

Traumatic brain injury patients are likely to have many other pathologies; thus, a clinical decision may be made to use a specific drug for PTP that may not be licenced. To ensure the trial remains pragmatic, the drug used for PTP can be based on hospital guidelines/clinician discretion, even if its use is deemed unlicensed. However, from our survey of 26 neuroscience centres in the UK, the most used LMWH for VTE prophylaxis in patients with TBI.

Patients enrolled on this trial can only be prescribed agents listed in this table.

7. Rationale of the trial

The overall aim of the TOP-TBI trial is to define best practices in the timing of venous thromboembolism prophylaxis in adult patients following a traumatic brain injury. We describe the trial below in the PICO format and in more detail thereafter.

Population	Adult (≥ 16 of age) patients who have sustained an acute traumatic brain injury and require admission to a hospital
Intervention	Early pharmacological thromboprophylaxis (PTP) administration (<72 hours from injury)
Control	Late PTP administration (prescription of PTP deferred by a minimum of 120 hours from injury or PTP not prescribed at clinical discretion)

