9.3.1 Early PTP administration trial arm

Upon randomisation, patients will be administered a PTP agent within 72 hours of injury. The agent will continue to be administered until a clinical decision to stop. The VTE prophylaxis agent used route of administration and dose will be as per local hospital practice. The treating team will be encouraged to follow NICE guidance regarding the type and initiation of mechanical VTE prophylaxis.

Following multi-stakeholder discussions, including patient representatives, we decided the definition of early PTP administration as being at any time point up to 72 hours from TBI. This cut-off is also supported by the existing literature and by the findings of our survey. There is also mechanistic evidence to support this threshold for initiation - previous work highlights a 24-48h time point as the transition period for trauma-induced coagulopathy from a hypo-coagulable state to a hyper-coagulable one (32,33). Our group of clinical stakeholders agreed that this time period allows the necessary time to consider other injuries and interventions, facilitate interval brain imaging as necessary and provide the necessary assurance on clinical trajectory.

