9.3.4. Randomisation

A secure web-based randomisation service (Sealed Envelope) will be used for the randomisation of eligible patients. Suitably trained staff will access the secure website and enter the necessary information. The system will provide an immediate allocation along with the patient identifier number for the trial. A confirmatory email will be sent to the email addresses of the study team members at the site randomising the patient. Trial investigators (or delegates) from the central team will be available 24-hours in case of problems or queries with the randomisation system. The presence of extracranial injury and initial admission to the ward vs critical care will stratify allocation. Stratified block randomisation will be used.

Early PTP arm - defined as administration of PTP within 72 hours of TBI

Late PTP arm - defined as administration of PTP after a minimum of 120 hours from TBI or PTP not administered at clinical discretion. PTP should not be administered within 120 hours and administration will be recorded as protocol deviation

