- a) Suitable to act as the legal representative by virtue of their relationship with the adult, and
- b) Available and willing to do so

For the purposes of sites in Scotland, a legal representative is defined as:

- a) Any guardian or welfare attorney who has the power to consent to the adult's participation in research
- b) If there is no such person, the adult's nearest relative as defined in section 87(1) of the Adults with Incapacity (Scotland) Act 2000

The patient's legal representative is not available in the hospital

Due to the condition of these patients, there will be those who will have no known legal representative or where the legal representative is not contactable or not able to visit the hospital at short enough notice to be able to enrol the potential participant within the required 72 hour time frame. In such cases, we advocate enrolment would be possible with written agreement from an independent clinician. If no legal representative is available for discussion, then an independent clinician (Independent Healthcare Professional) will be approached. If a legal representative visits the hospital later, then the trial will be discussed with them, and their consent sought at that time point to continue in the trial.

Participants who regain capacity whilst in the hospital will be informed about the clinical trial, and consent to continue will be sought. If, at any stage, either the legal representative or the participant chooses to withhold consent, then the participant will be withdrawn from the trial.

Participants who regain capacity following discharge will be contacted by phone and posted a PIS and ICF as soon as possible to complete and return to trial team.

Independent healthcare professional (IHP) definition

For the purposes of the TOP-TBI trial, the Independent Healthcare Professional (IHP) is defined as:

A person who is not connected with the conduct of the trial, specifically:

- a) The sponsor of the trial.
- b) A person who undertakes activities connected with the management of the trial.
- c) An investigator of the trial or,
- d) A health care professional who is a member of the investigator's delegated team for the purposes of the trial.

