11.4 Screening and Baseline Assessments

All participants will have a medical history taken and a clinical examination as part of the routine standard care. The following are to be recorded in the CRF:

- Inclusion/exclusion criteria review
- Informed consent process followed and consent or authorisation for enrolment obtained (signed consent form sent to the trial coordination centre for verification within 24 working hours)
- Routine review of clinical laboratory results
- ECG (if indicated by local policy)
- Standard of Care:
 - Patient medical history (including co-morbidities and relevant medications, including use of anticoagulation)
 - If pre-existing anticoagulation is present, the timing of any reversal agents used
 - Patient demography
 - Injury-related events - date of TBI, date of possible intubation, other injuries
 - Neurological status
 - Imaging review

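### Randomisation may take place up to the same 72-hour limit from injury by which the early arm must already have been dosed, so eligibility and the early-arm definition need to be reconciled

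*Protocol*

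**What the plan says.** Eligibility and the early arm are both timed from injury.

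- **Eligibility.** Protocol 9.1 admits "Patients admitted to hospital within 72 hours of injury". Section 9.2 excludes a patient if "The time interval from injury to randomisation exceeds 72 hours". Section 11.2 speaks of being able to "enrol the potential participant within the required 72 hour time frame". The schedule of assessments (Table 2, section 11.6) places screening, consent and randomisation within 72 hours of injury.
- **Early arm.** The PICO table in section 7 gives "Early pharmacological thromboprophylaxis (PTP) administration (<72 hours from injury)". Section 9.3 has patients "randomly assigned to the early pharmacological thromboprophylaxis (PTP) administration arm (<72 hours)". Section 9.3.1 states "Upon randomisation, patients will be administered a PTP agent within 72 hours of injury". Section 9.3.4 has "Early PTP arm - defined as administration of PTP within 72 hours of TBI". Table 2 gives the early treatment phase the same 72-hour limit as randomisation.
- **Late arm.** PTP is withheld until at least 120 hours from injury (9.3.2, 9.3.4). A late-arm dose before 120 hours is a protocol deviation.
- **Analysis.** Section 15.1 analyses all randomised patients as allocated, whatever their compliance.
- **Timing data.** The baseline list in 11.4 has "Injury-related events - date of TBI, date of possible intubation, other injuries".

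**The concern.** Consent comes before randomisation (11.2) and the early-arm dose comes after it, yet the last permitted time for randomisation and the last permitted time for the dose are the same. No section leaves an interval between them or asks that a dose still be feasible when the patient is randomised. The wording also differs: the exclusion applies above 72 hours, two early-arm definitions are strictly below 72, and two say within 72.

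An early-arm patient first dosed after 72 hours meets neither arm's definition if the dose falls before 120 hours. Section 9.3.2 names separation of the interventions as a design aim, and this erodes it from one side only: a late-arm patient randomised at 71 hours can comply in full. Under intention to treat the difference is pulled towards zero.

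A smaller, related matter is that eligibility and both arms are defined in hours, while the baseline list asks only for a date of injury.

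**Working it through.** **1. The two limits side by side.** Time left for dosing = 72 h − time of randomisation.

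| Randomised at | Eligible under 9.2? | Time left for the early dose |
|---|---|---|
| 72 h | Yes (72 does not exceed 72) | 0 h; the under-72 definition cannot be met |
| 71 h | Yes | 1 h; depends on how fast a dose can be given |

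Under 9.1, admission itself may occur at up to 72 h, before consent and randomisation have started.

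**2. The protocol's sample size (15.3).** Inputs: 10% late versus 5% early, 90% power, 5% significance (sidedness not stated; two-sided assumed), 1:1 allocation. Pooled normal approximation without continuity correction:

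n per arm = [1.960 × √(2 p̄(1−p̄)) + 1.282 × √(p₁(1−p₁) + p₂(1−p₂))]² / (p₁−p₂)²

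For 10% versus 5%, p̄ = 0.075 and n = [1.960 × √0.13875 + 1.282 × √0.1375]² / 0.05² ≈ 581.1, rounded up to 582 per arm, or **1164** in total, as stated. For 12% versus 7% the formula gives 1442 (stated 1441). For 10% versus 5.4% it gives 1408 (stated 1441). Inflating for loss, 1441/0.95 = 1517 (stated 1512). All agree within 3%, and none of this is in dispute.

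**3. Dilution.** Let q be the share of the early arm randomised too late to be dosed in time. The protocol gives no distribution of time to randomisation, so q is an assumption. As an upper bound, give these patients the full late-arm risk:

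early-arm risk = 5% + q × 5%; difference = 5% × (1 − q)

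Power = Φ{[(p₁−p₂)√n − 1.960 √(2 p̄(1−p̄))] / √(p₁(1−p₁) + p₂(1−p₂))}, with n = 1441/2 = 720.5 per arm.

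| q | Early-arm risk | Difference (points) | Power, 1441 evaluable | Total N for 90% power |
|---|---|---|---|---|
| 0 | 5.00% | 5.00 | 95.1% | 1164 |
| 5% | 5.25% | 4.75 | 92.5% | 1308 |
| 8% | 5.40% | 4.60 | 90.7% | 1408 |
| 10% | 5.50% | 4.50 | 89.2% | 1480 |
| 15% | 5.75% | 4.25 | 85.0% | 1684 |
| 20% | 6.00% | 4.00 | 80.0% | 1930 |

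Interpolating between 8% and 10%, power reaches 90% at about 8 + 2 × (90.7 − 90)/(90.7 − 89.2) ≈ 8.9%. At q = 8% the difference equals the 4.6-point fallback effect named in 15.3.

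**4. A milder assumption.** If patients dosed soon after 72 hours keep half the effect (risk 7.5%), q = 20% gives 0.8 × 5% + 0.2 × 7.5% = 5.5%, and power is 89.2%.

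**5. Timing.** The two arm boundaries are 120 − 72 = 48 hours apart. A date without a time leaves the moment of injury uncertain by up to 24 hours, half that gap.

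**The case against.** Several stronger readings are tempting, and the protocol does not support them.

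- *Late-randomised patients cannot comply.* This is strictly true only at 72 hours. Before that it is a practical matter. Section 10.3.1 allows ward stock and requires no trial-specific dispensing, so supply delay may be short, and no section ties the first dose to a drug round.
- *Sites are told to use the whole window for consent.* Section 11.2 does the reverse: it brings in an independent clinician when a representative cannot be reached in time. Section 9.3.3 asks for prompt screening after admission.
- *The affected patients are the sicker ones.* No section says who is randomised late, and unstable patients may be excluded under 9.2 where the clinical team lacks equipoise.
- *Eligibility and adherence cannot be checked.* Compliance is taken from inpatient records (10.3.2), medical notes are source data (16.2), and the eligibility review is recorded (11.4). Partial checking is possible.
- *The trial is underpowered.* The sample size is not wrong. The step from 1164 to 1441 absorbs a modest share even in the worst case, and some non-adherence is normal in a pragmatic trial.

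These points limit the size of the problem. They do not remove the coincidence of the two limits or the mismatch at exactly 72 hours. The headroom also has other purposes: 15.3 sets 1441 against a 12% late-arm rate or a smaller effect, and at 12% versus 7% power is already 90.0% with no dilution.

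**Conclusion.** The inconsistency stands on the text. Following the protocol as written admits avoidable non-adherence in the early arm alone, and the primary analysis carries it into the estimate. Its extent is unknown. The power loss is an upper bound that assumes no benefit at all in the affected patients, a late-arm rate of 10%, an effect of 5 points in everyone else and 1441 evaluable patients. On those terms the loss matters only once the share passes about 8–9%, and nothing in the protocol indicates that it will. This is a worthwhile, cheap improvement and no threat to the validity of the randomised comparison.

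**What to change.** The sponsor should reconcile 9.1, 9.2 and Table 2 with section 7, 9.3, 9.3.1 and 9.3.4, including strictly-under against within or up to 72 hours, so that every patient eligible at randomisation can still meet the early-arm definition. Which limit is right is for the sponsor; this review takes no position. One way that leaves the treatment window untouched is an item on the web randomisation form on which the site enters the time of injury and confirms that an early allocation could still be met.

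In 11.4, replace the date of injury with date and time, add a flag for estimated times, and record the time of the first PTP dose.

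The cost is one randomisation-form item, a few eCRF fields and small wording changes. The downside is that a few patients presenting in the last hours may be lost to recruitment.
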